4.5 Participant Registration

A signed informed consent form (ICF) and a Health Insurance Portability and Accountability Act (HIPAA) authorization must be obtained before any study-specific assessments are initiated. An electronic copy of the signed ICF will be given to the participant and a copy will be filed in the medical record. The original will be kept on file with the study records.

All participants consented to the study will be registered in OnCore®, the UCSF Helen Diller Family Comprehensive Cancer Center Clinical Trial Management System (CTMS). The system is password protected and meets HIPAA requirements.

Each participating site is responsible for OnCore® registration of study participants consented at the site.

4.6 Assignment to Intervention

This is a single-arm study. All participants will receive the 12-week adaptive text message intervention.

5 Study Intervention

We aim to develop a dietary intervention that will continuously adapt text message content and timing based on factors that may include: participants' sociodemographic characteristics, dietary behavior, and engagement with the text messages.

Our theoretical framework is based on the Capability Opportunity Motivation-Behavior (COM-B) model which states that individuals' behaviors are the result of interactions between their capabilities, opportunities, and motivations. Applying the model to whole grain intake, CRC survivors must have:

- 1) capability – the physical ability to consume whole grains without side effects (e.g., gas, bloating, bowel frequency); knowledge and skills to select and prepare whole grains; and psychological capability to resist cravings and control urges for refined grains;
- 2) opportunity – whole grains must be available, affordable, and socially acceptable; and
- 3) motivation – motivated to eat whole grains and develop a plan for doing so.

Intervention Components

Adaptive text messages using reinforcement learning (RL)

After completing baseline assessments, all participants will receive text messages for 12 weeks. Most days, participants will receive 1-2 messages. Text messages will be sent through the HealthySMS Platform and Twilio. Message content will target COM-B components of capability, opportunities, and motivations. The RL model will use a bank of text messages to target COM-B constructs. For example, to address psychological capability, messages will increase knowledge of what foods are recommended and how to prepare them. Behavior change techniques will include providing information, feedback, self-monitoring, and prompts/cues to increase knowledge. To address physical opportunity, text messages will focus on how to economically shop for and prepare whole grain foods. Behavior change techniques will include restructuring the physical environment, prompts/cues, instruction, feedback, and self-monitoring.

We will use the most up-to-date approaches for our RL model. For example, this may include a multi-armed bandit algorithm that predicts the outcome or "reward" (e.g., eating whole grains the previous day [yes/no], or servings of whole grains eaten on the previous day) based on action variables (e.g., whether to send a message, message type) and contextual variables (e.g., individual characteristics, whole grain intake yesterday/past week). RL algorithms "explore" what text messages to send by sending messages randomly at first and then "exploit" the information, so that over time, the algorithm sends more of the messages that predict more frequent intake of whole grains. In our proposal, participants' replies to daily text messages asking about their intake of whole grains on the previous day will be used as the "reward" data.

Participants' response rate to the daily question about whole grain intake is a primary outcome in this study. We will send a reminder message to participants who have not responded (e.g., "Please respond even if you ate 0 whole grains yesterday.") If participants do not respond a few days in a row, we will send a non-response message (e.g., "We haven't heard from you in a few days. Please respond to the text messages or contact our team at [study phone number].") If a participant does not respond for 7 consecutive days, we may invite them to a semi-structured

interview to understand reasons for non-response. Non-responders will continue to receive study text messages unless they request the messages be stopped (e.g., by texting back STOP or notifying the study team). All participants, including non-responders, will be asked to complete the surveys at 12 weeks to gather quantitative usability and acceptability data and estimate the effect of the intervention on diet behavior.

Educational material

At enrollment, all participants will receive printed materials defining the recommendations for whole grain intake, what is a whole grain, whole grain serving sizes, and cooking tips.

Intervention Components for Food Insecure Participants

We will use the Food Security module from the National Health Interview Survey to identify food insecure participants at enrollment. We will follow the standard of care at ZSFG for food insecure individuals: the study coordinator will provide a list of resources including food banks and meal delivery programs and facilitate application or SNAP benefits, if needed.

5.1 Delivery of Study Intervention

We will use REDCap, the HealthySMS platform (developed for prior work led by [name]), UCSF's Research Analysis Environment (RAE), and Twilio to conduct the proposed study. REDCap is a secure study management and database platform with mature features for online surveys and forms for data entry. HealthySMS is a web-based automated text messaging platform for use in health and social service settings, clinically and for research purposes. The system allows for scheduling of text messages to be sent automatically to individual patients or patient groups. It supports two-way communication between participants and researchers. The web-based platform enables the visualization of participants' data and contains a dashboard that allows for viewing data from multiple participants in one screen.

5.2 Interventionist Training and Tracking

Consistent implementation of the study protocol, measurements, and interventions is essential. Training manuals will be created. Data will be collected in REDCap through online surveys, HealthySMS and Twilio through text messages, recording of interviews on Zoom, and dashboards for study staff to enter data. We will monitor recruitment and study progress using a flow sheet template consistent with the CONSORT guidelines for reporting of feasibility trials to ensure we are meeting recruitment and retention goals. Members of the study team will meet weekly, or as needed, throughout the study.

5.3 Adherence Assessment

Intervention Adherence

Adherence to the intervention will be measured using number of replies to text messages that asked for a response.

Proposed Engagement Strategies for Retention

To prevent attrition, our study staff develop good rapport and open, responsive communication with participants. Participants will be provided with a phone number and email address to contact if they encounter issues with any aspect of the study. Staff will convey reminders of study tasks by phone, email, and/or text messages. Participants may be compensated with gift cards as described in Section 4.2. If a participant does not respond to a study-related request, up to five automated reminders will be sent and the study staff will reach out to the participant

via phone and/or e-mail. If we are unable to reach a participant after three more attempts, we will determine a participant lost to follow-up.

5.4 Participant Discontinuation/Withdrawal from the Study

Participants are free to withdraw from participation in the study at any time upon request.

An investigator may discontinue a participant from the study for the following reasons:

- Unacceptable adverse event(s)
- Lost-to-follow up; unable to contact participant (see Section 5.5 - Lost to Follow-Up)
- Any event or medical condition or situation occurs such that continued collection of follow-up study data would not be in the best interest of the participant or might require an additional treatment that would confound the interpretation of the study
- The participant meets an exclusion criterion (either newly developed or not previously recognized) that precludes further study participation

5.5 Lost to Follow-up

A participant will be considered lost to follow-up if he or she fails to reply to a study-related request after the study staff have sent the following attempts to contact:

- up to five automated email reminders
- study staff will reach out to the participant via phone and/or e-mail up to three more times

These contact attempts will be documented in the participant's study file. Should the participant continue to be unreachable, he or she will be considered to have withdrawn from the study with a primary reason of lost to follow-up.

6 Study Procedures and Assessments

6.1 Schedule of Activities

Period/Procedure	Screening/Baseline	Study Intervention Period	End of Study
	Visit -1 (D-84 to D1)	Weeks 1-12 (D1 to D84)	Study Week 12 (+/-84 days)
Administrative Procedures			
Consent ¹	X		
Medical Record Review, if available	X ²		
Inclusion/Exclusion Criteria	X		
Other Study Assessments			
Sociodemographic and Clinical Variables survey	X		
Adverse Events (Recent Health Survey) ³	X		X
Dietary Assessment Survey (FFQ)	X		X
Food Security Survey	X		X
Food Beliefs Survey (theoretical constructs)	X		X
Text Message Intervention Engagement ⁴		Throughout	
“Reasons for Non-Response” Interview		See Footnote 6	
System Usability Scale (SUS)			X
Acceptability of Intervention Measure (AIM)			X
Intervention Appropriateness Measure (IAM)			X
Feasibility of Intervention Measure (FIM)			X
End of Study Interview (optional)			X

1 DocuSign or paper copy mail with prepaid return envelope

2 Participants will be allowed to self-report their clinical information if no medical records are available (e.g., patients for whom we cannot obtain records).

3 Pre-existing expected adverse events (e.g., diarrhea, constipation, etc.) will be assessed at enrollment via a Recent Health Survey containing questions from PRO-CTCAE, and emergent events will be assessed at 12 weeks. Medical records may be collected in the event that an SAE is observed.

4 Measured via text message response

5 Food Security module from the National Health Interview Survey

6 Only for participants who do not respond to text messages; If a participant does not respond to text messages for 7 days, we will invite them to a semi-structured interview to understand reasons for non-response.

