2.1 Primary Objective

Primary Objective	Endpoint(s)	Time Frame
Determine the intervention's feasibility ¹ and acceptability ²	
• Participants' responses to text messages that ask for a response• Participant surveys• Semi-structured end of study interviews	From 0 to 12 weeks

1) The intervention will be determined feasible if the median response proportion to text messages that ask for a reply is $\geq 70\%$, and the median score for the Feasibility of Intervention measure is ≥ 4 .

2) The intervention will be determined acceptable if median scores on the Acceptability of Intervention and Intervention Appropriateness Measures are ≥ 4 .

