6.2.3 End of Study Intervention (Study Week 12 ± 84 days)

- 12-week surveys:
 - Dietary Assessment (FFQ)
 - Food Security module from the National Health Interview Survey
 - Theoretical constructs assessed using a modified Food Beliefs survey
 - Adverse events in past 12 weeks assessed by a Recent Health Survey, using questions from the NCI's Patient Reported Outcomes version of the Common Terminology Criteria for Adverse Events (PRO-CTCAE). Medical records may be collected in the event that an SAE occurs.
 - System Usability Scale (SUS)
 - Acceptability of Intervention Measure (AIM)

- Intervention Appropriateness Measure (IAM)
- Feasibility of Intervention Measure (FIM)
- End of study interview (optional)

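### The end-of-study survey window of Week 12 ± 84 days is as wide on each side as the whole intervention, conflicts with the 12-week endpoints, and has no matching analysis rule

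*Combined protocol and SAP*

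**What the plan says.** The window appears in two operative places. The schedule table in Section 6.1 heads the end-of-study column "Study Week 12 (+/-84 days", and the procedures text is titled "End of Study Intervention (Study Week 12 ± 84 days". Section 6.1 sets the intervention at Day 1 to Day 84 and the screening/baseline period at Day -84 to Day 1.

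Elsewhere the timing is 12 weeks, with no tolerance:

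- Section 2.1 gives the primary time frame as "From 0 to 12 weeks". Section 2.2 gives the same span for the change in percent whole grains and in fiber.
- Section 5 states: "All participants, including non-responders, will be asked to complete the surveys at 12 weeks".
- Footnote 3 to Section 6.1 says that "emergent events will be assessed at 12 weeks".
- Section 7.1 puts the FFQ at enrollment and week 12, and the usability, acceptability, appropriateness and feasibility scales at 12 weeks.
- Section 6.2.2 lists only message engagement and the non-response interview for Days 1 to 84.
- Section 9.2.2 compares intake before and after the intervention, at 0 and 12 weeks.

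Recall periods are fixed. The FFQ asks about the past 3 months (Section 7.1). The health survey is described in Section 6.2.3 as "Adverse events in past 12 weeks assessed by a Recent Health Survey", and Section 8.1 confirms the 12-week recall. Section 6.2.4 says that participants are not followed once the study intervention is discontinued. Sections 9.2.1 and 9.2.2 do not mention survey date.

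**The concern.** A tolerance normally lets a visit slip without changing what it measures. Here each side is as long as the intervention itself, so a survey can be in window and still not describe the 12 weeks of messaging.

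The surveys concerned are the Feasibility, Acceptability and Appropriateness measures (FIM, AIM, IAM), whose medians must reach 4 under Section 2.1, the FFQ behind both secondary endpoints, and the adverse-event survey. Because the recall periods are fixed, the completion date determines how much of each answer concerns the intervention. Staff following the schedule would record a badly timed survey as compliant, and the analysis sections say nothing about how to treat it. The text-message response criterion does not depend on this window.

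**Working it through.** **1. The window in days.** Week 12 ends on Day 84 (12 × 7) and begins on Day 78 (11 × 7 + 1). The window is 84 − 84 = Day 0 to 84 + 84 = Day 168. Days 0 and 1 also lie inside the baseline window of Day -84 to Day 1.

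**2. Share of recall that falls in the intervention.** A survey on day t with a recall of R days looks back over days t − R + 1 to t. The share is the number of those days between Day 1 and Day 84, divided by R. The adverse-event recall is R = 84. The protocol does not give 3 months in days, so for the FFQ I take 84 to 91.

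| Survey day | R = 84 (adverse events; FFQ lower reading) | R = 91 (FFQ upper reading) |
|---|---|---|
| 0 | 0% | 0% |
| 28 | 28/84 = 33% | 28/91 = 31% |
| 42 | 42/84 = 50% | 42/91 = 46% |
| 78 | 78/84 = 93% | 78/91 = 86% |
| 84 | 84/84 = 100% | 84/91 = 92% |
| 112 | 56/84 = 67% | 63/91 = 69% |
| 126 | 42/84 = 50% | 49/91 = 54% |
| 168 | 0% | 7/91 = 8% |

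**3. What off-time FFQs could do (illustration only).** From Section 9.1.1: change of 9 points, SD 23, alpha 0.05, and 60 participants with 20% dropout, so 60 × 0.8 = 48 completers. My assumptions: a two-sided paired t-test, a constant 9-point shift from Day 1, SD unchanged, all other surveys at Day 84, and the survey dates shown. Recorded change = 9 × mean share. Power comes from the noncentral t distribution with noncentrality (change/23) × √48.

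| Survey dates assumed | Recorded change (R = 91 to R = 84) | Power |
|---|---|---|
| All at Day 84 | 8.3 to 9.0 | 69 to 76% |
| 1 of 48 at Day 42 | 8.2 to 8.9 | 68 to 75% |
| 2 of 48 at Day 42 | 8.1 to 8.8 | 67 to 74% |
| 12 of 48 at Day 42 | 7.3 to 7.9 | 57 to 64% |

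Example for two surveys with R = 84: 9 × (46 × 1 + 2 × 0.5)/48 = 8.81, a loss of 0.19 points. The 76% in the first row falls short of the 80% stated in Section 9.1.1, but that gap comes from the sample-size inputs and not from the window.

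**4. The late side.** The effect on the FFQ depends on what diet does after messages stop. If all 48 surveys were spread evenly over Days 78 to 168, full reversion to old habits gives 4.8 to 5.0 points (power 29 to 32%), and full persistence gives 8.9 to 9.0 points (about 75%). For adverse events the loss needs no such assumption: beyond Day 84 the recall simply misses intervention days.

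**5. Analysis rules.** Sections 9.2.1 and 9.2.2 contain no minimum exposure, no assignment of surveys to a window, no use of survey date and no timing sensitivity analysis.

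**The case against.** The strongest reply is that Week 12 is the target everywhere and ± 84 days is only a generous tolerance. The surveys are listed as end-of-study, 12-week surveys. Section 6.2.2 schedules none of them during Days 1 to 84, and Section 9.2.2 speaks of intake before and after the intervention. A late allowance also has a visible purpose: Section 5.3 says "up to five automated reminders will be sent", Section 5.5 repeats "up to five automated email reminders", and both add up to three further contacts. Finally, this is a single-arm proof-of-concept trial, and a few early scores would seldom move a median across 4.

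Most of this stands. A reader might infer from the literal window that the trial plans to take post-intervention surveys from people with little or no exposure. The documents do not support that, since everything except the two window statements points to Week 12 or later. A reader might also take the larger losses above as expected bias. They rest on survey dates that I assumed, and no passage suggests that 12 of 48 people would answer at Day 42 or that surveys would spread evenly to Day 168. Nor do late FFQs necessarily dilute the change; they do so only if diet reverts.

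The reply does not remove the conflict. No passage overrides the stated window, contact attempts do not explain an early side, and the late side has to be squared with Section 6.2.4. That section could be read as covering only people who stop early, but it does not say so.

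**Conclusion.** The point holds as an internal inconsistency that should be fixed. The window is Day 0 to Day 168, its early side is probably a drafting fault, and its late side extends to where recall covers none (adverse events) or 0 to 8% (FFQ) of the intervention. These shares are arithmetic from the protocol's own days and recall periods, apart from the 84-to-91-day reading of 3 months.

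The size of any bias cannot be determined, because no survey dates are given. With only a few off-time surveys it would be small: one or two at Day 42 cost about 0.1 to 0.2 points and 1 to 2 percentage points of power under the assumptions above. The case for change rests on the conflict and on how cheaply it can be removed, not on a forecast loss.

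**What to change.** - **Sections 6.1 and 6.2.3:** replace ± 84 days with a window that opens at Study Week 12 (about Day 78) and has a stated late limit, just long enough for the reminders and contacts in Sections 5.3 and 5.5. Those sections give no durations, so the study team must set the limit.
- **Section 6.2.4:** reconcile it with that limit, so that collecting surveys shortly after the last message is clearly allowed.
- **Dates:** record the completion date of every end-of-study survey, including the adverse-event survey, and report the timing.
- **Sections 9.2.1 and 9.2.2:** treat the FFQ and FIM/AIM/IAM alike. Keep all completed end-of-study surveys in the main analysis, and let the all-scores median decide the criteria of 4 or higher. Early surveys may come from people who stop, so dropping them could favour the intervention. Add one sensitivity analysis limited to in-window surveys.

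The cost is one IRB-approved amendment under Section 10.4, the recording of dates and a little more analysis. No completed survey is lost. The sensitivity analysis may be small and may favour prompt responders, so it should be read as descriptive.

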1.5 Risks/Benefits

Potential Risks

The risks involved in this study are few. There is a minor risk of loss of confidentiality, either through the breach of data collected via the Internet or text messaging or through the breach of secure study databases, physical files, etc. Dietary modifications may result in changes in bowel function, including but not limited to diarrhea, constipation, increased urgency, flatulence, and/or bloating. These changes are not expected to be clinically significant but could impact quality of life if they occur.

Potential Benefit of the Proposed Research to Participants and Others

The benefits of healthy diet are well established. Intervention participants may experience decreases in symptom burden and improved physical functioning and quality of life. This study will produce societal benefit regarding knowledge about how to optimize a text message-based intervention to improve diet quality in cancer survivors. Given the minimal risk of study participation and potential benefits, the risks to participants are reasonable in relation to the anticipated benefits to society.

Procedures used to minimize risk

- Numerous studies have demonstrated that healthy diet is safe, feasible, and beneficial for cancer patients and survivors.
- Participants will receive tips on how to alleviate or avoid digestive changes due to increased whole grain and fiber intake.
- Participants will be asked to contact the study team at any time if they have questions or concerns about the study.

- All study files, folders, and records will be kept in locked file cabinets that can be accessed only by study personnel.
- All data will be exchanged over an SSL-protected connection, and all data will be encrypted.
- The study database and all survey data will be collected and stored in REDCap, the HealthySMS platform, Twilio, and UCSF's Research Analysis Environment (RAE), which have protections needed for storage of PHI.

Limited private identifiable information necessary for the conduct of the study will be collected in the proposed research project. For example: names, phone numbers, and email addresses. This information will be stored securely in REDCap, the HealthySMS platform, Twilio, and UCSF's Research Analysis Environment (RAE; mytransfer.ucsf.edu), which have the protections in place and approvals for the storage of PHI.

Importance of Knowledge to be Gained

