6.2.4 Follow-up

Participants will not be followed after discontinuing the study intervention.

7 Reporting and Documentation of Results

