8.1 Definition of Adverse Event (AE)

An adverse event (AE) is defined as any untoward medical occurrence associated with the use of an intervention in humans, whether or not considered intervention related.

Adverse event assessment:

A Recent Health Survey with modified questions from the NCI Patient Reported Outcomes version of the Common Terminology Criteria for Adverse Events (PRO-CTCAE) Measurement System will be used to collect AEs by self-report in study participants. The survey measures participant-reported frequency, severity, and interference of expected symptoms and also allows the participant to report the severity of unexpected symptoms. Most symptoms are graded on a 5 point Likert scale ranging from 0 to 4. Frequency responses are assessed by the question "How often do you have [symptom]?" and include: Never, Rarely, Occasionally, Frequently, and Almost constantly. Severity responses are assessed by the question "What was the severity of your [symptom] at its worst?" and include: None, Mild, Moderate, Severe, Very Severe. Interference responses are assessed by "How much did [the symptom] interfere with your usual or daily activities?" and include: Not at all, A little bit, Somewhat, Quite a bit, and Very much. For this study, assessments of frequency, severity, and interference are based on a 12-week recall period.

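### The plan does not require the symptom survey when a participant withdraws or is discontinued, so reachable leavers have no assured post-baseline record of non-serious symptoms.

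*Combined protocol and SAP*

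**What the plan says.** Non-serious symptoms are collected by self-report on the Recent Health Survey, which is built from PRO-CTCAE questions (7.1, 8.1). Footnote 3 of 6.1 covers pre-existing symptoms at enrollment and then states "questions from PRO-CTCAE, and emergent events will be assessed at 12 weeks". Sections 6.2.1 and 6.2.3 list the survey at those two points. Section 6.2.2, covering Days 1 to 84, lists text engagement and, where applicable, the non-response interview. Section 8.1 adds that "assessments of frequency, severity, and interference are based on a 12-week recall period".

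On leaving, 5.4 lets participants withdraw at any time and lets an investigator discontinue someone, with an unacceptable adverse event among the listed reasons. Section 5.5 defines loss to follow-up after up to five automated reminders and up to three further staff contacts. Section 6.2.4 says: "Participants will not be followed after discontinuing the study intervention".

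On people who stay but fall silent, Section 5 says "All participants, including non-responders, will be asked to complete the surveys at 12 weeks".

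On the symptoms themselves, 1.5 warns: "Dietary modifications may result in changes in bowel function". It adds that these changes are not expected to be clinically significant.

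**The concern.** Someone who leaves in week 3 may have left because of bloating or urgency, or for an unrelated reason. The plan has a survey that would help tell these apart, but nothing requires staff to offer it at that moment. Data on emergent symptoms would then come mainly from people who stayed.

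This limits what can be said about tolerability. Bowel changes are the main physical risk named in 1.5. Section 5 also makes eating whole grains without digestive side effects part of capability, one of the three constructs the messages target. Section 9.2.1 will summarise attrition, and 1.4 says the results will inform a later randomized trial. Whether leavers had bowel symptoms is useful for designing that trial, and it is hard to recover once they have gone.

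**Working it through.** The plan states no figure on this point, so the check is mainly of the text.

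**Step 1. Is a symptom survey required at exit?**

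| Section | What it provides | Does it ask a leaver about symptoms? |
|---|---|---|
| 6.1, 6.2.1, 6.2.3, 7.1 | Survey at enrollment and end of study | Not at exit |
| 6.2.2 | Text engagement; non-response interview | No |
| 5.4 | Withdrawal and discontinuation rules | No |
| 5.5 | Contact attempts before a person is declared lost | No |
| 6.2.4 | No follow-up after stopping the intervention | No |
| 6.1, 6.2.3 | End-of-study window of 84 days either side of week 12 | Permits an early survey; does not require one |

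**Step 2. Does another route close the gap?**

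| Section | Route | Why it falls short |
|---|---|---|
| 1.5, 5.3 | Participants can contact the team; staff keep communication open | Depends on the person volunteering symptoms |
| 5; 6.1 footnote 6 | Interview after 7 days without a reply | About reasons for not replying; not triggered by withdrawal |
| 5 | Week-12 surveys for all, including text non-responders | Does not mention people who have withdrawn or been discontinued |
| 8.5 | Medical management until resolved or stabilized | Applies to events already known |
| 8.6 | CRF documentation and reporting of serious events | Not aimed at non-serious symptoms |
| 10.5, 10.6, 10.8 | CRFs, case histories, site calls | Places to record a reported event; none asks the question |

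None of these routes requires staff to ask a reachable leaver about symptoms.

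**Step 3. What would an exit survey capture?** Inputs: messages start on Day 1 (6.1), and recall is 12 weeks (8.1), or 12 × 7 = 84 days. A survey on exit Day d, with d no later than 84, covers the 84 days ending on Day d. It therefore includes all d days on messages, and 84 − d recall days fall before they began.

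- Exit on Day 14: 84 − 14 = 70 of 84 days predate the messages.
- Exit on Day 42: 84 − 42 = 42 of 84 days predate the messages.

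The two exit days are illustrations. An exit survey never misses time on messages, but an early leaver's answers mix it with a longer earlier period. They can only be read next to that person's baseline survey.

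**The case against.** The strongest reply is that this is a preference. Feasibility and acceptability are defined in 2.1 by text response and three questionnaire scores. The secondary and exploratory endpoints are diet and message mix. Section 9 plans no adverse event analysis, and 8.4 classes the study as minimal risk. All of this stands, and it keeps the point minor. It does not supply the missing question.

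Four stronger readings are tempting, and the documents do not support them.

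- A reader might infer that people discontinued for an adverse event leave no trace. An investigator can act only on an event already known. That event can be recorded under 10.5 and 10.6 and is followed under 8.5.
- A reader might apply the 20% drop-out in 9.1.1 to the 60 participants and treat the result as the number without a symptom record. That allowance belongs to the diet power calculation. It does not separate reachable leavers from people lost to follow-up, whom an exit survey would rarely reach.
- A reader might take 6.2.4 to exclude people who merely stop their texts from the week-12 surveys. Section 5 asks everyone for those surveys, and 6.2.4 more naturally means that there is no follow-up phase after the study.
- A reader might see the wide end-of-study window as part of this gap. Late completion is a separate matter, which an exit survey does not address.

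It is also fair to say that an exit request asks something more of people exercising a right to leave, and that it yields few, variably timed answers with no control arm. That is why it should be a single voluntary request.

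**Conclusion.** The gap is real and small. Reachable participants who withdraw or are discontinued have no assured post-baseline record of non-serious symptoms, unless they volunteer them or the event is already known. The conclusion rests on the absence of any exit requirement in 5.4, 5.5, 6.1 and 6.2.4, and on the other routes recording or managing events without asking about them.

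The number of people a change would help cannot be derived from the documents and may be only a few. The documents do not support a claim of bias in any planned result, or of any effect on the primary or secondary endpoints. The point is worth considering because the instrument already exists and the information is hard to obtain later.

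**What to change.** In the 6.1 footnote and in 6.2.4, state that each reachable participant who withdraws or is discontinued will be asked once, voluntarily, to complete the existing Recent Health Survey at exit, online or on the paper copy that 7.1 already allows. Report these answers separately from the week-12 surveys, with the study day of completion and beside the person's baseline answers. Give the number of leavers with no exit survey.

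The cost is a short amendment signed by the investigator and approved by the IRB (10.4), one more use of a survey already in REDCap, and a little staff time. Some leavers will decline, and timing will vary. People lost to follow-up will mostly stay missing. For early leavers, much of the recall period predates the messages, so the answers will be descriptive only.
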